#### 8. STUDY ASSESSMENTS AND PROCEDURES

- Study procedures and their timing are summarized in the SoA (Table 2). Protocol waivers or exemptions are not allowed.
- All screening evaluations must be completed and reviewed to confirm that potential subjects meet all eligibility criteria. The Investigator will maintain a screening log to record details of all subjects screened and to confirm eligibility or record reasons for screening failure, as applicable.
- If multiple assessments are scheduled at the same timepoint, it is recommended that procedures be performed in the following sequence: 12-lead ECGs, vital signs, sample collection for lipids, other laboratory and PD biomarker tests, sample collection for PK and prior to administration of study drug.
- Immediate safety concerns should be discussed with study Medical Monitor immediately upon occurrence or awareness to determine if the subject should continue or discontinue IP.
- Adherence to the study design requirements, including those specified in the SoA (Table 2), is essential and required for study conduct.
- Procedures conducted as part of the subject's routine clinical management (e.g., blood count) and obtained before signing of the ICF may be utilized for subject management and pre-screening, however screening and baseline assessments must be obtained by central laboratory and as defined by the protocol.
- Any situation at the site level with potential impact on subject safety or study conduct, including situations related to COVID-19 infection or control measures, should be discussed with the Sponsor/contract research organization (CRO) immediately upon occurrence or awareness to determine potential impact on study subject/s or study conduct.

## 8.1. Efficacy Assessments

Fasting blood samples will be collected at the time points specified in the SoA for the measurement of serum total lipids, lipoprotein profiles, and apolipoproteins. Efficacy assessments in this study are the PD and biomarker assessments, which are described in Section 8.6.

## 8.2. Safety Assessments

Safety assessments include AEs (either reported by the subject or observed by the Investigator), concomitant medication use, physical examination, ECG, vital signs, and laboratory assessments.

Any clinically significant safety assessment findings, including physical examination, ECG, vital signs, laboratory assessments, and AEs that are considered to be related to COVID-19 infection should be documented as such in the AE term reported (e.g., COVID-related pneumonia).

All safety analyses will be performed using the Safety Analysis Set (Section 9.4.5). Planned time points for all safety assessments are provided in the SoA (Table 2).

#### 8.2.1. Physical Examinations

- A complete physical examination will include, at a minimum, assessments of the cardiovascular, respiratory, abdominal and a neurological exam. Height (only collected at screening) and weight will also be measured and recorded.
- A symptom directed physical examination will include, at a minimum, assessments of the skin, respiratory, cardiovascular system, and abdomen (liver and spleen).

#### 8.2.2. Vital Signs

- Vital signs including body temperature, pulse rate, RR, and supine BP will be assessed.
- Planned time points for vital signs assessment are provided in the SoA (Table 2).
- Starting from randomization, BP and pulse will be measured in duplicate. The first measurement will be initiated before dosing with sitting/semi-erect or supine position and resting for at least 5 minutes prior to measurements. BP and pulse are to be repeated at least 1 minute apart. Additional vital signs measurement may be done if clinically indicated.

#### 8.2.3. Electrocardiograms

- 12-lead ECG will be recorded as single bedside measurements using an ECG machine that automatically calculates the heart rate and measures PR, QRS, and QT (QTcF) intervals.
- Subject to be resting for at least 2 minutes prior to ECG.

#### 8.2.4. Clinical Safety Laboratory Assessments

- See Appendix 2 (Section 10.2) or the list of clinical laboratory tests to be performed and the SoA (Table 2) for the timing and frequency. Laboratory tests should be performed under fasting conditions (for at least 12 hours; it is recommended that subjects fast no more than 14 hours). Subjects should be instructed to attempt to remain consistent in how long they fast prior to blood draws for the duration of the study.
- Fasting is defined as taking nothing by mouth except non-mineral water (and any essential medications). It is required that subjects abstain from consumption of alcoholic beverages for at least 48 hours before laboratory test assessments.
- The Investigator must review the laboratory report, document this review, and record any clinically relevant changes occurring during the study in the AE section of the eCRF. The laboratory reports must be filed with the source documents. Clinically significant abnormal laboratory findings are those which are not associated with the underlying disease, unless judged by the Investigator to be more severe than expected for the subject's condition.
- Retesting of laboratory tests is allowed when results are deemed spurious or incomplete.
- All laboratory tests with values considered clinically significantly abnormal during participation in the study or within 28 days after the last dose of IP should be repeated

until the values return to normal or baseline or are no longer considered clinically significant by the Investigator or the Medical Monitor.

- If such values do not return to normal/baseline within a period of time judged reasonable by the Investigator and remain clinically significant, the etiology should be identified and the Medical Monitor notified.
- All protocol-required laboratory assessments, as defined in Appendix 2 (Section 10.2), must be conducted in accordance with the relevant study manual and the SoA (Table 2).
- If laboratory values from non-protocol specified laboratory assessments performed at the institution's local laboratory require a change in subject management or are considered clinically significant by the Investigator (e.g., SAE or AE or skipping of dose), then the results must be recorded in the eCRF and the Medical Monitor should be notified.

#### **8.3.** Adverse Events and Serious Adverse Events

The definitions of an AE or SAE can be found in Appendix 3 (Section 10.3).

Adverse events will be reported by the subject (or, when appropriate, by a caregiver, surrogate, or the subject's legally authorized representative).

The Investigator and any qualified designees are responsible for detecting, documenting, and recording events that meet the definition of an AE or SAE and remain responsible for following up AEs that are serious, considered related to the IP or study procedures, or that caused the subject to discontinue the study or IP (see Section 7).

#### 8.3.1. Time Period and Frequency for Collecting AE and SAE Information

The timing and frequency of collection of all AEs and SAEs is specified in the SoA (Table 2).

Table 4 summarizes the different reporting periods for AEs, SAEs and events to monitor. Events to monitor are defined in Section 10.3.3.

**Table 4:** Adverse Event Reporting Periods

| Type of
Event                   | Adverse Event   | Serious Adverse Event   | Events to Monitor with Investigational Product                     |
|------------------------------------|---|---|---|
| Reporting period                   | From consent until 28 days after last dose of investigational product | From consent until 28 days after the last dose of investigational product | From consent until 28 days after the last dose of investigational product |
| Reporting
Timelines to
89bio | Entered into the clinical database on an ongoing basis                | Within 24 hours   | Within 24 hours   |

All SAEs will be recorded and reported to 89bio or designee immediately and under no circumstance should this exceed 24 hours, as indicated in Appendix 3 (Section 10.3). The

Investigator will submit any updated SAE data to 89bio or designee within 24 hours of it being available.

Investigators are not obligated to actively seek AEs or SAEs after conclusion of the study participation. However, if the Investigator learns of any SAE, including a death, at any time after a subject has been discharged from the study, and he/she considers the event to be reasonably related to the IP or study participation, the Investigator must promptly notify 89bio or designee.

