| HIV, HCV and HBV Serology l         |   | x   |                            |                                  |   |   |   |   |   |   |   |   |                        |
| FSH if required to determine menopausal status |   | X   |                            |                                  |   |   |   |   |   |   |   |   |                        |
| Serum pregnancy test (WOCBP)                   |   | X   |                            |                                  |   | _ |   |   |   |   |   |   | X                      |
| Urine pregnancy test (WOCBP)                   |   |   | X                          | X                                |   |   |   | X |   |   |   | X |                        |

[figure not shown]
|   | Schedule of Assessments   |   |                            |                                  |   |   |   |   |   |   |   |   |                        |
|---|---|---|----------------------------|----------------------------------|---|---|---|---|---|---|---|---|------------------------|
| Study Period (Duration)   | Screening/
Lifestyle
Stabilization
(Min
4 weeks to
Max
6 weeks) | Screening/
TG
Qualification
(2 Week) | Screening/
TG
Sample | Double-blind Treatment (8 Weeks) |   |   |   |   |   |   |   |   | Follow-up
(4 Weeks) |
| Visits  |   |   |                            |                                  |   |   |   |   |   |   |   |   |                        |
| Study Day b  |   |   |                            |                                  |   |   |   |   |   |   |   |   |                        |
| Jug dispensed for 24-hour urine collection for cortisol and creatinine m |   |   | Х                          |                                  |   |   |   |   |   |   | x |   |                        |
| Archived serum and plasma samples n                                      |   |   |                            | x                                |   |   |   | х |   |   |   | X |                        |
|   |   |   |                            |                                  |   |   |   |   |   |   |   |   |                        |
| Investigational product dosing p   |   |   |                            | X                                | X | X | X | X | X | X | X |   |                        |

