| AE and SAEs including
hypersensitivity-related AEs q                  | х   | X   |                            | х                                |   |   |   | X |   |   |   | X | X                      |
| Concomitant medication  | х   | X   |                            | Х                                |   |   |   | Х |   |   |   | Х | X                      |
| Review of lifestyle and alcohol use r                                    | х   | X   | х                          | X                                |   |   |   | Х | х |   | х | X | x                      |
| MRI-PDFF    |   |   |                            | X                                |   |   |   |   |   |   |   | X |                        |
| FGF21   |   |   |                            | X                                |   |   |   |   |   |   |   |   |                        |

[figure not shown]
Shaded columns indicate visits that can be conducted by home health providers.

Abbreviations: AE = adverse event; ; ALT = alanine aminotransferase; ALP = alkaline phosphatase;

ApoB = apolipoprotein B100; ; aPTT = activated partial thromboplastin time; AST = aspartate aminotransferase;

; BP = blood pressure; BMI = body mass index; BUN = Blood urea nitrogen; CK = creatine kinase; CKD-EPI = chronic kidney

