## 6.4. Measures to Minimize Bias: Randomization and Blinding

Eligible subjects will be randomized in the order they are enrolled into the study. Subjects in the main cohort will be randomized in a 1:1:1:1:1 ratio to 1 of 4 doses of BIO89-100 (9 mg QW, 18 mg QW, 27 mg QW, or 36 mg Q2W) or placebo. Subjects in the fibrate expansion cohort will be randomized in a 1:1 ratio to BIO89-100 27 mg or placebo QW.

To maintain the blind, each subject will receive 2 injections QW including subjects randomized to 36 mg Q2W who will receive placebo injections at alternate Q2W visits.

Randomization in the main cohort will be stratified by TG <750 mg/dL or ≥750 mg/dL (8.47 mmol/L) and by whether or not the subject is receiving background therapy (e.g., prescription fish oil and/or statins). Randomization in the fibrate expansion cohort will be stratified by TG <750 mg/dL or ≥750 mg/dL (8.47 mmol/L) only. All subjects will be centrally assigned to randomized IP using an Interactive Voice/Web Response System (IVRS/IWRS). Before the study is initiated, the log-in information and directions for the IVRS/IWRS will be provided to each site.

The study will be conducted under double-blind conditions. The subjects, PI, other study personnel involved with subject assessments, and 89bio will remain blinded to the actual treatment

assignments of the subjects, post-baseline lipid panels (TG, , , LDL-C, HDL-C, Non-HDL-C, VLDL-C, VLDL-TG, , ApoB, , , RPL-C, , and PK data. Blinded IP will be provided by a clinical supplies vendor and shipped to the study site. IP may be delivered to the subject's home for home administration by an HHP. The SC administration of the blinded IP will be performed by trained study staff, and only blinded staff will be involved with subject assessments.

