#### 8.3.2. Method of Detecting AEs and SAEs

The method of recording, evaluating, and assessing causality of AEs and SAEs and the procedures for completing and transmitting SAE reports are provided in Appendix 3 (Section 10.3).

Care will be taken not to introduce bias when detecting AEs and/or SAEs. Open-ended and non-leading verbal questioning of the subject is the preferred method to inquire about AE occurrences.

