#### **10.3.3.** Definition of Events to Monitor

#### 89bio-defined Events to Monitor for BIO89-100:

Events to Monitor include hypersensitivity reactions occurring after the first administration of study agent(s) in subjects participating in this clinical study. These events must be reported by the Investigator to 89bio within 24 hours and are to be considered serious (for regulatory reporting purposes) only if they meet the definition of an SAE. The events are to be reported on an SAE form

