g = History of drug and/or alcohol abuse taken at screening [REDACTED] only. Urine drug test will be performed at [REDACTED] only. h= Alcohol breathalyzers will be used. Results >0.01% will be considered as positive.

i = [REDACTED]

j = [REDACTED]

[REDACTED]  
[REDACTED]  
[REDACTED]  
[REDACTED]  
[REDACTED]  
[REDACTED]

iii. [REDACTED]  
[REDACTED]

k = Subjects will be included in either the Intensive PK scheme (optional) or Trough PK scheme (all subjects). [Table 5 in the protocol](#) details sampling times for the Intensive PK scheme. Intensive PK subjects will have additional visits on [REDACTED]. For the Trough PK scheme, blood samples will be taken within 4 hours prior to dosing on specified dosing days or during EOT visit [REDACTED] for all subjects.

Note: Where the Intensive PK schedule overlaps with the Trough PK schedule, only 1 PK measurement should be taken at those time points.

l = Serology tests will include HBsAg, HCV, and HIV 1 and 2 antibodies. HBV and HCV determined by antibodies first and, if positive, by DNA/RNA.

m = Ambulatory 24-hour urine collection for analysis of cortisol and creatinine to be initiated the day prior to [REDACTED]. Subject will start collection 24 hours before coming into the clinic and bring the sample to the visit. The 24-hour urine collection jug is dispensed at [REDACTED] so collection can be completed and brought to [REDACTED], respectively. The jug may be provided at the site or by an HHP.

n = Archived for possible analysis of additional biomarkers. This is optional and by subject consent.

o = [REDACTED]  
[REDACTED]  
[REDACTED]

[figure not shown]
p = Subjects randomized to BIO89-100 36 mg Q2W group will receive BIO89-100 at [REDACTED] and placebo at [REDACTED] to maintain the blind. Home health IP administration may occur on [REDACTED].

q = When IP is scheduled to be administered by an HHP, a subject's spontaneous reports of AE/SAE will be reported to the site staff who will follow-up and evaluate the need for an unscheduled visit for AE assessment. The sites/HHP may take non-personally identifying photographs of potential injection site reactions (optional).

r = Study coordinators should reinforce maintenance of eating and exercise habits without weight loss or gain of 5% for the duration of the study, and alcohol consumption restrictions 48 hours prior to fasting blood work.

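### The Schedule of Assessments marks adverse-event and hypersensitivity enquiry at only 2 of the 8 dosing visits; at the other six, capture depends on what the subject volunteers

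*Protocol*

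**What the plan says.** Protocol section 8.3.1 names a single source for when AEs are collected: "The timing and frequency of collection of all AEs and SAEs is specified in the SoA (Table 2"). No other section sets a second schedule.

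That table (Protocol section 1.2) has one row for "Investigational product dosing" and one for AEs and SAEs including "hypersensitivity-related AEs". Dosing is weekly in every arm, since section 6.4 says that "each subject will receive 2 injections QW", with placebo on the alternate visits of the 36 mg Q2W group.

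Three other provisions bear on the point:

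- Section 8.3.2, on method: "Open-ended and non-leading verbal questioning of the subject is the preferred method to inquire about AE occurrences".
- Footnote q to the AE row, read from the SAP's copy of the schedule (Appendix 1), on doses given by a home health provider: "a subject's spontaneous reports of AE/SAE will be reported to the site staff who will follow-up" and consider whether an unscheduled visit is needed.
- Section 10.3.3, on hypersensitivity reactions, the sponsor's defined Events to Monitor: "These events must be reported by the Investigator to 89bio within 24 hours".

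Footnote c, also from SAP Appendix 1, describes the physical examination marked at dosing visits as symptom-driven and performed for AEs already reported.

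**The concern.** An AE schedule normally follows contact with the subject: if a trained person is there to inject, the subject is asked how the last dose went. Here the governing table leaves that question out at most dosing visits, so a site that follows the plan to the letter has no scheduled enquiry for weeks at a time. The other routes by which an AE could reach the record begin only once the subject has mentioned something.

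The events at risk are the mild and short ones. Section 2.2.3 lists injection site reactions (all Grade 1), headache, contact dermatitis and nausea as the most common events in the first-in-human study. The frequency of treatment-emergent AEs is a listed safety endpoint (Protocol section 3). SAP section 4.4.1 classifies these events by onset date and time and by worsening of grade, details that are harder to recover weeks later. Section 10.3.5 also expects severity to be assessed at onset. The 24-hour clock for hypersensitivity helps only from the moment the investigator learns of the event.

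**Working it through.** There is no power or sample-size figure to reproduce. The check is a count of marks in Protocol Table 2, whose rows have 13 visit columns. Visit and day headings are redacted, so columns are identified by position. Column 4 carries both the randomisation mark and the first dosing mark. The dose number is therefore the column number minus 3, for columns 4 to 11.

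| Row in Protocol Table 2 | Columns marked | Dosing visits covered |
|---|---|---|
| Product dosing | 4-11 | doses 1-8 |
| AE/SAE including hypersensitivity | 1, 2, 4, 8, 12, 13 | doses 1, 5 |
| Concomitant medication | 1, 2, 4, 8, 12, 13 | doses 1, 5 |
| Physical examination | 1-13 | doses 1-8, all symptom-driven (footnote c) |
| Lifestyle and alcohol review | 1-4, 8, 9, 11-13 | doses 1, 5, 6, 8 |
| Lipid sampling | 2-4, 8, 9, 11-13 | doses 1, 5, 6, 8 |
| Trough PK, all subjects | 4, 5, 6, 8, 12 | doses 1, 2, 3, 5 |

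**Overlap of AE enquiry and dosing.** {4-11} ∩ {1, 2, 4, 8, 12, 13} = {4, 8}, so 2 of 8 dosing visits carry the mark. The six without it are columns 5, 6, 7, 9, 10 and 11, which are doses 2, 3, 4, 6, 7 and 8.

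**Longest planned gap.** From dose 1 to dose 5 is (5 - 1) × 7 = 28 days, against 7 days if every dosing visit were marked. The same three-visit gap recurs after dose 5: doses 6, 7 and 8 are unmarked, and the next mark is column 12, the end-of-treatment visit.

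**Are the blanks explained by absent staff?** No. Someone injects at every one of these visits. At doses 6 and 8 the same table also schedules a lifestyle and alcohol review and lipid sampling, and at doses 2 and 3 a trough PK sample from all subjects. A subject can thus be interviewed about alcohol at dose 6 with no AE question scheduled.

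**Do the other provisions supply the question?** Taken in turn:

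- Footnote c: the examination responds to a reported AE, so it follows a report and does not prompt one.
- Footnote q: it covers home-health dosing only and passes on spontaneous reports.
- Section 8.3.3: proactive follow-up starts after the initial report.
- Table 4 in section 8.3.1: it fixes the period during which AEs are reportable, from consent to 28 days after the last dose, but schedules no enquiry.

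None of them schedules the questioning that section 8.3.2 prefers.

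**The case against.** The strongest reply is that a blank cell does not mean an absence of safety oversight. AEs are reportable continuously and entered on an ongoing basis. Every dosing visit carries a symptom-driven examination covering at least skin, respiratory and cardiovascular systems and abdomen (section 8.2.1). Immediate safety concerns go at once to the Medical Monitor (section 8). Section 8.3.2 states a preference and assigns it to no visit, so the schedule does not formally contradict it. Home-dosing details sit in a study manual that is not public and may contain a prompt.

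Much of this stands. It shows that a subject can report an event at any weekly contact, so it would be wrong to say that the record rests wholly on four-week recall. It does not show that anyone is scheduled to ask.

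Several stronger readings are tempting, and the documents do not support them:

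- *Nobody is scheduled to ask about any reaction to dose 1 until dose 5.* The first dosing visit is itself marked for AEs, and section 6.2 has subjects rest about 15 minutes after injection. The documents do not say whether that AE entry comes before or after the dose, so immediate reactions may be captured. The gap is clear only for reactions that start after the subject leaves.
- *The primary safety endpoint is compromised.* No safety endpoint is called primary; AE frequency is one of several.
- *Losses fall mainly on active arms, so differences are understated.* All arms have two blinded injections weekly on one schedule, and no figure gives the share of events lost in any arm.
- *Home-dosed and site-dosed visits are ascertained differently.* The row is blank at these six visits in both settings, and nothing shows that site-dosed subjects are asked.
- *Some 756 dosing visits go without the question.* 6 × 126 = 756 is an upper limit that assumes full enrolment and complete dosing. The planned main cohort alone gives 6 × 90 = 540. The plan allows for about 10% loss to follow-up (section 9.2), and SAP section 5.5 reports low enrolment in the fibrate cohort.

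**Conclusion.** The point holds in a limited form. The governing schedule marks AE/hypersensitivity enquiry and concomitant medication at 2 of 8 dosing visits. For the other six it relies on reports that the subject volunteers and on an examination that such reports trigger. That is weaker ascertainment than the questioning preferred in section 8.3.2. Reactions that begin after the first dosing visit may go unasked about for up to about 28 days, and mild, short events may be under-recorded. The size of the loss, and whether it differs by arm, are unknown.

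The count depends on column positions in the Protocol's table. The SAP copy has partly collapsed columns and was used only for the footnotes. Reading the two marked visits as Day 1 and Week 4 is an inference from position and weekly dosing; the 2-of-8 count does not depend on it. Sites may ask at every visit in practice, but the plan does not require it. This is a worthwhile, cheap improvement to ascertainment and does not undermine the trial's conclusions.

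**What to change.** 1. In Protocol Table 2 and SAP Appendix 1, mark the AE/SAE/hypersensitivity and concomitant-medication rows at all eight dosing visits.
2. Have whoever injects, site staff or home health provider, ask the open-ended question of section 8.3.2 at each dosing visit and pass any positive answer to the site.
3. Reword footnote q so that it covers answers to that question as well as spontaneous reports, and reconcile footnote c so that the symptom-driven examination visibly follows from the enquiry.

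This changes ascertainment only; what is done about a reported event stays under the existing sections. The cost is two row edits, two footnotes and one worksheet line, with no new visit or staff. The downside is slightly more recording work and a few more minor AEs in all arms. If conduct is too far advanced to amend, the study report should state the enquiry schedule beside the AE tables as a limit on the reported rates.
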